## **Investigational Medicinal Product (IMP) and Matching Placebo: Dronedarone (Multaq®)**

---

### *Dronedarone (Multaq®)*

Dronedarone HCl ( $C_{33}H_{44}N_2O_5S$ ) is a white powder and benzofuran derivative that is practically insoluble in water, yet freely soluble in methanol and methylene chloride. The mechanism of action is unclear. Dronedarone exhibits properties of all four Vaughn-Williams antiarrhythmic classes, but the contribution of each of these activities to the clinical effect is unknown. Bioavailability of dronedarone is about 4% without food. It increases to 15% when dronedarone is administered with a high fat meal. Please see **Appendix C: Abbreviated Investigational Medicine Product Insert**, for more information.

### *Dronedarone (Multaq®) or Matching Placebo Packaging and Labeling*

A single panel, English only label will be applied to each bottle. Dronedarone, or Multaq®, 400 mg are provided as oblong shaped, white film-coated tablets for oral administration. Each tablet is engraved

---

 All pertinent investigational product (IP) information was obtained from the “**Highlights and Prescribing Information**” for dronedarone (Sanofi Pharmaceuticals) in Appendix B.

with a double wave marking on one side and the code “4142” on the other side. Dronedarone will be provided in bottles containing 60 tablets only. Packaging and labeling will be standardized across all study sites.

#### *Dronedarone (Multaq®) or Matching Placebo Storage and Handling*

All packages are stored at 25°C (77°F) with excursions permitted between 15°C and 30°C (or between 59°F and 86°F).

#### *Dronedarone (Multaq®) or Matching Placebo Disposal*

The destruction of all used and unused units delivered by McKesson will be the responsibility of study sites. Sites will be responsible for destroying the drug with oversight from their lead pharmacy. Recommendations for proper disposal may vary based on instituted laws. If a site does dispose of dronedarone, each site will dispose of dronedarone in accordance with the state and federal regulations. Site based documentation of IP destruction and/or disposal should be provided to Tulane University, Academic Research Organization (ARO). Tulane University ARO will provide Sanofi with documentation of destruction of all unused or partially used product.

#### *Dronedarone (Multaq®) and Matching Placebo Dose and Dosing Regimen*

Dronedarone or a matched dose of placebo will be administered orally twice a day for 12 months. The placebo used in this trial is a physical match to the drug product. The study participant will be required to document medication regimen adherence on paper or on an electronic drug diary.

The trial drug should be taken after a meal. It should also be taken with a large glass of water (~250 mL) and consumed over as short a time as possible. Study participants should be instructed to swallow the capsules whole and not chew them. Study participants who are randomly assigned to the treatment group will take two 400 mg dronedarone (Multaq®) tablets each day. Those assigned to the control group will take two placebo tablets each day. Please refer to the “**Dose Administration by Group Assignment**” table below for more information.

If the study participant forgets to take the scheduled dose, s/he should not take the dose more than 4 hours after the usual time and should continue treatment the next day. Any missed doses should be skipped altogether and should not be replaced or made up at the next scheduled dosing.

Dose Administration by Group Assignment		
Assigned Group:	Number of Study Participants:	Dose:
Treatment Group	n=165	400 mg dronedarone (Multaq®), taken orally twice a day for 1 year
Control Group	n=165	400 mg of placebo taken orally twice a day for 1 year

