### *Dosing and IMP Administration*

Drug/placebo therapy starts the same day after the ablation procedure. A 3-month supply will be provided to all participants. Dronedarone 400mg or an oral placebo tablet will be administered twice daily (morning and evening) along with substantial meals. No dosing adjustment is needed in cases of mild renal impairment. Any adjustment to treatment would be considered a secondary endpoint and will not prompt an interruption in subsequent follow-up visits and assessments. Study participants will continue to be followed for primary and other secondary endpoints.

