## B. General Considerations for Data Analysis

Data analysis will be conducted to address the research questions. All statistical tests will be two-sided with a  $p \leq 0.05$ . Descriptive statistics such as, mean (SD) for continuous variables and frequency (%) for categorical variables will be provided for baseline information. The simple t-test/Wilcoxon rank sum test or chi-square tests will be applied to compare the demographic information and the baseline clinical measurements between the intervention and control groups to assess if randomization is successful at each site. Any imbalanced information will be included in the regression models to account for potential confounding variables in assessing treatment effects. All primary efficacy analysis will be performed in an intent-to-treat (ITT) manner.

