### *Analysis of LA Fibrosis Progression*

The primary outcome variable will be changes in the percentage of fibrosis from baseline, 3- and 12-months via CMR assessments in patients randomized to receive dronedarone vs. placebo.

We will apply models for longitudinal data to analyze the LA fibrosis progression over the follow-up period. The two most popular approaches for longitudinal data are the Linear Mixed-effects Model approach (LMM) and Generalized Estimating Equations (GEE). The LMM requires parametric assumption such as, normality on the random effects and model errors, and it is more powerful when the assumptions are met, but vulnerable to departures from the assumed distributions. GEE provides robust

estimates because it does not require any distribution assumption. Therefore, we will first investigate the distribution of the outcome, and if the distribution assumption is reasonable, we will use LMM model, otherwise, we will use GEE approach. Due to the clustering effect at a physician level, we will use random effects in LMM or working correlation in GEE model to account for the correlations. In all the models, the primary predictor is the intervention condition. We will also consider controlling other potential confounders if the data exhibits any. The intervention effect is assessed by the estimated coefficient of the primary predictor. The coefficient with right direction and a p value  $<0.05$  indicates there is a significant intervention effect.

Per standard principles, the primary analyses will be done on an intention to treat basis (ITT), treating all randomized patients with available outcome data regardless of compliance. A Robustness Analysis will include a per protocol analysis, where only those patients who actually received their assigned treatment (e.g., those who received dronedarone per the dosing protocol) will be analyzed. In terms of missing data, the survival analysis approach to the AF recurrence outcome will censor any patients who drop out of the study without AF recurrence at the time of their last known contact. While we would propose such patients to have their first documented recurrence date counted as their failure date, alternative analysis approaches for the analysis of interval-censored data will also be considered for robustness.

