## 2 DOSAGE AND ADMINISTRATION

The recommended dosage of MULTAQ is 400 mg twice daily in adults. MULTAQ should be taken as one tablet with the morning meal and one tablet with the evening meal.

Treatment with Class I or III antiarrhythmics (e.g., amiodarone, flecainide, propafenone, quinidine, disopyramide, dofetilide, sotalol) or drugs that are strong inhibitors of CYP3A (e.g., ketoconazole) must be stopped before starting MULTAQ [*see Contraindications (4)*].

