#### Administration Instructions

Page 45 of 49

Version 4.0:  
Revision Date: April 27th, 2022

Copyright© April 2022 Tulane University School of Medicine, Academic Research Organization on behalf of the Principal Investigator.  
All rights reserved.

[figure not shown]
TULANE UNIVERSITY  
Academic Research Organization

MULTAQ should be administered with a meal. Warn patients not to take MULTAQ with grapefruit juice.

- If a dose is missed, patients should take the next dose at the regularly scheduled time and should not double the dose.
- Advise patients to consult a physician before stopping treatment with MULTAQ.

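### The missed-dose rule resumes treatment on the following day, which does not fit twice-daily dosing: after a missed morning dose it also drops that evening's tablet, contrary to Appendix C

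*Combined protocol and SAP*

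**What the plan says.** Dosing is twice a day for 12 months. The section Dosing and IMP Administration states that drug or placebo "will be administered twice daily (morning and evening) along with substantial meals", and Appendix C (section 2, Dosage and Administration) agrees: "MULTAQ should be taken as one tablet with the morning meal and one tablet with the evening meal".

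The missed-dose rule is in the section Dronedarone (Multaq®) and Matching Placebo Dose and Dosing Regimen. A participant who forgets a dose "should not take the dose more than 4 hours after the usual time and should continue treatment the next day". The sentence after it adds: "Any missed doses should be skipped altogether and should not be replaced or made up at the next scheduled dosing". The same section sets up the adherence record: "The study participant will be required to document medication regimen adherence on paper or on an electronic drug diary".

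Appendix C, under Administration Instructions, has its own rule: "If a dose is missed, patients should take the next dose at the regularly scheduled time and should not double the dose".

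On the analysis side, section B (General Considerations for Data Analysis) states: "All primary efficacy analysis will be performed in an intent-to-treat (ITT) manner". The per-protocol robustness analysis, described under Analysis of LA Fibrosis Progression, takes as its example "those who received dronedarone per the dosing protocol".

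**The concern.** Resuming on the following day is the natural instruction for a once-daily drug. With a morning and an evening dose, it is right after a missed evening dose, because the next scheduled dose is then the next morning. After a missed morning dose, the next scheduled dose falls on the same evening, and a participant who follows the sentence as written leaves that one out as well.

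Two things are at stake. The first is avoidable under-dosing in a regimen that participants take themselves at home for a year. The second is the record. After a missed morning dose it is unclear whether the evening tablet was due, so a diary entry for that evening can be scored as adherent or not. A per-protocol set that refers back to the dosing protocol inherits the same ambiguity.

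**Working it through.** There is no figure in the plan to reproduce. The check is a comparison of the instructions, followed by a small count of tablets and hours.

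**Comparing the instructions**

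| Event | Dosing-regimen section, read literally | Appendix C |
|---|---|---|
| Morning dose missed (more than 4 h late) | Resume next morning; evening dose also omitted | Evening dose taken at its normal hour, not doubled |
| Evening dose missed | Resume next morning | Resume next morning |

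The 4-hour window is not part of the conflict. It defines when a dose counts as missed, and Appendix C is silent on that. The second sentence of the protocol rule forbids making up a missed dose at the next dosing. That agrees with Appendix C on doubling but does not say when to resume. The only words in that section that do say so point to the following day.

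**Per event**

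Assumption: doses at 08:00 and 20:00. The documents say only morning and evening.

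- Day-1 morning dose missed, Appendix C rule: last dose 20:00 on day 0, next dose 20:00 on day 1. Gap 24 h, 1 tablet lost.
- Day-1 morning dose missed, literal protocol rule: last dose 20:00 on day 0, next dose 08:00 on day 2. Gap 36 h, 2 tablets lost.
- Day-1 evening dose missed, either rule: last dose 08:00 on day 1, next dose 08:00 on day 2. Gap 24 h, 1 tablet lost.

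**What the longer gap means**

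Appendix C (section 12.3) gives an elimination half-life of 13 to 19 h. Under simple exponential decay, the fraction remaining is 0.5^(gap / half-life):

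- 24 h: 0.5^(24/13) = 0.278 and 0.5^(24/19) = 0.417, so about 28% to 42%.
- 36 h: 0.5^(36/13) = 0.147 and 0.5^(36/19) = 0.269, so about 15% to 27%.

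This illustrates the direction and rough scale. It is not a pharmacokinetic prediction.

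**Per year**

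Tablets due: 2 × 365 = 730. Extra tablets lost through the wording = number of misses × share that are morning doses. The documents give no miss rate, so both inputs are assumed, and the literal rule is taken to be followed every time.

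| Assumed misses per year | Morning share | Extra tablets lost | Share of 730 |
|---|---|---|---|
| 12 (one a month) | one half | 12 × 0.5 = 6 | 0.8% |
| 52 (one a week) | one half | 52 × 0.5 = 26 | 3.6% |
| 12 | all | 12 × 1 = 12 | 1.6% |
| 52 | all | 52 × 1 = 52 | 7.1% |

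With half the misses in the morning, total loss rises from 12 to 18 tablets (1.6% to 2.5%) at one miss a month, and from 52 to 78 (7.1% to 10.7%) at one a week.

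**The case against.** The strongest reply is that the literal reading is not how a sensible person would take the rule as a whole. It concerns a single forgotten dose, only missed doses are to be skipped, and the evening dose has not been missed. The section also requires two tablets a day, and Appendix C, to which the protocol sends readers for more on the drug, already gives the right answer. This has force: many participants would take the evening tablet. It does not remove the conflict, because no clause ranks Appendix C above the body of the protocol, and the body's only statement on resuming points the other way. Nor does the protocol give any reason for withholding the evening dose.

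Several narrower points stand:

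- The participant's own instruction sheet and diary are not in the documents, so what participants are actually told is unknown.
- The per-protocol set is described by example, with no adherence threshold, so it cannot be shown that one disputed tablet would move anyone in or out of it.
- Compliance is reviewed at 3, 6, 9 and 12 months, and returned drug is recorded, so total intake can be estimated under either reading. Those counts do not show whether a given evening dose was due.
- The yearly range rests on assumed inputs. The upper end needs 52 missed mornings, no missed evenings, and the evening dose left out each time. Only the per-event result is firmly supported.

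**Conclusion.** The concern holds as a minor one. Followed as written, the rule gives the wrong action after a missed morning dose: one further tablet lost and a gap of about 36 h where Appendix C would give about 24 h, assuming 12-hour spacing. After a missed evening dose the two rules agree. The yearly cost depends on a miss rate that the documents do not give; 0.8 to 3.6 percentage points of adherence is an illustration under the stated assumptions. Any effect on the endpoints cannot be quantified from the documents and is probably small. The sample size, the alpha level and the intention-to-treat primary analyses are untouched.

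**What to change.** In the dosing-regimen section, replace the clause that resumes treatment on the following day with the Appendix C rule: the participant takes the next dose at its normal hour and does not double it. Keep the 4-hour window as the definition of a missed dose. Put the same wording in the participant dosing instructions and make the diary consistent with it, so that the evening dose after a missed morning dose is plainly due.

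The cost is one clause at the next amendment and a short note to sites. No visits, procedures, participants or analyses change.

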### *Dronedarone (Multaq®) and Matching Placebo Dose Administration*

Based on their assigned study arm, study participants will receive either drug or placebo at two different timepoints during the study on-site. A 3-month supply of dronedarone or placebo will be dispensed after their cardiac ablation. (i.e. upon randomization). At their 3-month visit and/or at additional in-person visits, a 9-months supply (or remaining bottles of dronedarone or placebo) will be dispensed to all participants. During dispensation an additional bottle (1-month supply) of IP/Placebo may be provided to account for months with different number of days and/or to have extra in case of any unforeseen changes (e.g. extreme weather conditions causing delays in receiving drugs, IMP/Placebo loss or damage etc.) Please refer to the “**Investigational Product Administration Schedule**” below.

Investigational Medicinal Product and Placebo Administration Schedule		
Study Timepoints:	Study Arm #1: Drug	Study Arm #2: Placebo
Day of Cardiac Ablation (i.e. upon randomization)	3-months' supply of dronedarone (Multaq®) given to study participant on site	3-months' supply of placebo given to study participant on site
3- Month Visit and/or at additional visits	9-month supply or remaining supply of dronedarone (Multaq®) given to study participant on site	9-month supply or remaining supply of placebo given to study participant on site

### **IMP Safety Considerations**

#### *Accountability for Investigational Medicinal Product and Matching Placebo*

The investigational medicinal product and matching placebo will be distributed to each trial site via McKesson (distribution center). Only participants enrolled in the study may receive study drug and only authorized site staff may supply or administer the study drug. The site investigator, institution or the head of the medical institution (where applicable) is responsible for ensuring adequate accountability of all used and unused drug and placebo. This includes acknowledgement of receipt of each shipment of the trial drug (quantity and condition).

Each trial site must keep an investigational medicinal product and matching placebo accountability record that capture:

- The date when the drug and placebo was received/dispensed
- Participant ID
- Lot Number
- Expiration Date
- Quantity of bottles received/dispensed
- Balance
- The date and quantity of used and unused IMP/Placebo returned to the site
- The destruction
- The initials of the person recording this information

### **Concomitant Medications**

Page 19 of 49

Version 4.0:  
Revision Date: April 27th, 2022

Copyright© April 2022 Tulane University School of Medicine, Academic Research Organization on behalf of the Principal Investigator.  
All rights reserved.

TULANE UNIVERSITY  
Academic Research Organization

Concomitant use of the following is prohibited in all patients, regardless of treatment arm and needs to be discontinued at a minimum of 24 hours prior to receiving the first dose of trial treatment:

Use of strong CYP 3A inhibitors, such as ketoconazole, itraconazole, voriconazole, cyclosporine, telithromycin, clarithromycin, nefazodone, ritonavir, or drugs or herbal products that prolong the QT interval and might increase the risk of Torsade de Pointes, such as phenothiazine antipsychotics (e.g. prochlorperazine, chlorpromazine, fluphenazine, trifluoperazine, and thioridazine) tricyclic antidepressants (e.g. clomipramine, amitriptyline, nortriptyline, desipramine, imipramine, and doxepin) certain oral macrolide antibiotics (e.g. erythromycin, roxithromycin, azithromycin, and clarithromycin), and Class I (e.g. quinidine, procainamide, disopyramide, mexiletine, lidocaine, and tocainide) and III antiarrhythmics (e.g. sotalol, amiodarone, and dofetilide).

Medication history and current medication use will be assessed at all study related time points. Please refer to the “**Study Schedule**” and “**Schedule of Events**” sections for outlines of appropriate study procedures for each specific study timepoint.

## **Study Procedures and Data Elements**

---

### *Clinical Site Selection*

All EDORA recruiting sites will be pre-screened for eligibility. Prior to trial initiation, sites must have adequate recruitment potential and the proper infrastructure for fibrosis imaging (ability to perform CMRs). However, based on site recruitment and enrollment patterns (e.g. low enrollment, etc.), other suitable sites may be approached for study inclusion. Training materials providing detailed descriptions of MRI acquisition and image submissions will be developed and provided to each site accordingly.

### *Pre-Study Start Up*

Six to eight months will be allotted for developing trial materials, IRB approvals, start-up activities, and patient enrollment. If a site needs to extend the enrollment period, they must first seek approval from Tulane University ARO.

### *Study Duration and Close Out*

This study will span 13 months with the study participant receiving 12 months of study drug plus an additional one month of continuous ECG monitoring. In other words, approximately 13 months will be for follow-up after the last patient has been randomized into a treatment arm.

An additional 6 months is needed for data cleaning and validation, analysis, and other close out activities such as manuscript preparation.

Tulane University ARO may keep trial related information (e.g. biological sample results, ECG readings and reports, MRI scans and reports) for up to 7 years after the end of the clinical trial.

### **Pre-screening**

#### *Recruitment/Patient Identification Process*

Patient recruitment will occur at all pre-screened participating centers. Participants may also be recruited from the community by direct advertising; emails, TV, flyers posted in public places, as well as online postings to study-site affiliated websites, social media platforms (Facebook, Twitter, and Instagram) and LinkedIn. The enrollment period is expected to last between 6 to 8 months. Patients

Page 20 of 49

Version 4.0:  
Revision Date: April 27th, 2022

Copyright© April 2022 Tulane University School of Medicine, Academic Research Organization on behalf of the Principal Investigator.  
All rights reserved.

TULANE UNIVERSITY  
Academic Research Organization

will be introduced to the trial by their treating physician during clinic visits. Investigators will have medically pre-screened these individuals for suitability to enter the clinical trial at their clinic visit. A one-page summary of the trial can be provided to patients at their visit informing them on how to participate should they wish to do so.

## **Screening Visit**

### *Study Eligibility Assessment*

The inclusion and exclusion criteria will be assessed by reviewing patient medical charts and during the verbal interview at the screening visit by a designated study site team member. All pre-screened medical eligibility must be documented as verified by the site investigator.

### *Informed Consent*

The consent process begins from the time the patient has been identified and contacted for recruitment. Once the patient has met the eligibility criteria for the study, the site investigator or delegated study staff will provide a full description of the research purpose and personnel, procedures involved, risks and benefits, and reiterate that partaking in this clinical trial is completely voluntary. The patient will be informed of any change to risk throughout the course of the trial. It may be necessary to re-consent the patient to ensure that they are fully informed and still agree to participate. Any associated study costs and compensation, if applicable, will also be provided. Patients will be given sufficient time to read and sign the consent form and the study staff member obtaining the informed consent will answer any questions posed by the patient. If during the trial re-consenting is needed, the most current and approved informed consent form may be sent to participants for electronic review and signature.

